# **10 DATA PROCESSING AND MANAGEMENT**

## ***10.1 Data Management System***

Data are entered by the clinical centers using a web data entry application that directly enters study data into the CoC's study database. The web application guides the clinical site staff member through the data entry process. If an invalid response is entered, the website signals and provides a message about the error and how to solve it. At any point during entry, the staff member can make an electronic note concerning a particular response. Valid individual responses are saved as soon as they are entered. The system includes programmed skip patterns as required by the case report forms, and also includes quality control checks such as lists of valid values for multiple choice items. The system provides automated consistency checking so the study staff can resolve inconsistencies quickly without a lengthy communication with the CoC. The same checking is also run on the central database at the CoC to verify that centers are resolving consistency checks.

## ***10.2 Data Transfer***

Newly entered clinical center data are received by the CoC immediately upon data entry. The CoC merges newly received data with the accumulated data in a SAS database. Data transfer from central units such as the central laboratory will be through the CoC data management system.

## ***10.3 Quality Control***

Range checks, inter-item checks, cross-table checks, and double data entry verification are used where appropriate to ensure accurate data entry. Specific quality control procedures are run to check for missing, incorrect, and questionable values immediately after they are entered. Reports with the necessary patient identifying information and the problem values are printed and sent to the clinical centers for correction or verification. When returned, corrected values are entered and checked again for consistency with other items. The goals are to make quality control a continuous process, to make the turnaround time between error detection and correction as short as possible, and to document any changes made to the database.

## ***10.4 Back-up, Data Security and Confidentiality***

The CoC adheres to the George Washington University Biostatistics Center's data backup and security policies to ensure the safety and confidentiality of the data. Backup procedures include: twice-weekly system backup, daily incremental backup, and off-site disaster recovery backup. Security procedures include: logon and link password protection, and for internet access, separate Web servers which use SSL and encryption algorithms. Virus and malware protection software is used on all computers and is updated on an hourly basis. All portable computers employ full disk encryption. George Washington University computing facilities provide support in the event of a disaster. Access to the server and databases is secured by use of login user accounts and passwords. Remote access is granted only to authorized users and is accomplished using a secure virtual private network (VPN). Appropriate filtering/firewall setup is used to prevent unauthorized access.

## ***10.5 Tracking Study Progress***

The purpose of tracking reports is to keep the collaborative group informed of study progress, and to report special problems and resolutions. Reports will be produced regularly by the CoC, as directed by the Steering Committee. These reports will be distributed to the study group through the study website.

Tracking reports include the following types of information:

**CONFIDENTIAL**

- screening and enrollment (versus goal), by clinical center, gender, and race/ethnicity
- tables describing adherence to the study protocol (attendance at scheduled study visits, study intervention compliance)
- database inventory
- number of data edit queries generated and outstanding, by clinical center
- progress of analysis and manuscripts

## **10.6 Archiving and Study Close-out**

At the end of the study, after all data have been received and edited, the database will be archived in computer readable format, including documentation files, files of study documents (such as forms annotated with variable names, protocols, and manuals of procedures), data files in the form of SAS transport files and input statements, data dictionaries, and program code documenting any derived variables. After the study is complete, all data will be available to RISE study investigators and to investigators from outside the study in a manner consistent with the NIDDK's data distribution procedures. Data will be stored at a readily accessible, password-protected website.

# **11 STUDY ADMINISTRATION**

This randomized clinical trial is one of three studies conducted by the RISE Study Consortium. RISE is a collaborative study group funded by the NIDDK of the National Institutes of Health (NIH) under a cooperative agreement mechanism. The goal of the RISE Study is to test different interventions to preserve  $\beta$ -cell function in separate trials, with shared procedures and data collection approaches allowing for the ability to compare data across studies and combine data from individual studies by harmonizing study outcomes and data collection. The RISE Study investigators will be conducting three separate clinical trials. The investigators for each trial are responsible for recruiting participants and implementing their respective protocols. In addition, the RISE Study investigators participate in consortia activities, as described below.

## **11.1 Organization**

The major organizational components and their responsibilities are described:

- The *RISE Steering Committee*, comprised of the principal investigators of the clinical centers, the CoC, and the NIDDK project office, is the primary decision making body for the study with overall responsibility for the design and conduct of the common elements of the study protocols.
- The *NIDDK project office* participates in all decision-making activities and selects and oversees the activities of the DSMB.

**CONFIDENTIAL**

- The *Coordinating Center (CoC)* located at the George Washington University Biostatistics Center operates under subcontract to the Seattle Institute for Biomedical and Clinical Research (SIBCR). The CoC has responsibility for coordinating the study, including production and distribution of materials and documents, set-up and administration of the data management system, maintenance of the central database, analysis of primary study results, distribution of final study data to the clinical centers and NIDDK repository, and reporting of results in collaboration with the other investigators.
- The *Central Blood Laboratory (CBL)* operates under subcontract to the Seattle Institute for Biomedical and Clinical Research. The CBL is responsible for providing procedures for the handling, storage, and shipment of blood specimens, for performing the tests and assays, for performing quality control, for providing patient-level reports to clinical centers, and for transferring results to the CoC.
- The *DSMB* is composed of outside experts in the design and conduct of clinical trials, and in type 2 diabetes. The board is responsible for reviewing the study documents, monitoring study progress, and monitoring patient safety.
- *Working committees* include Outcomes, Recruitment and Retention, Safety and Monitoring, Publications and Presentations, Ancillary Studies, Lab Quality Control, and Program Coordinators. Committees can be discontinued and additional committees can be created as required.

## **11.2 Central Laboratories and Reading Centers**

In collaboration with the CoC and study investigators, central laboratories and reading centers perform the following tasks:

1. Establish procedures and standards for training staff involved in the measurement, collection, preparation, handling, transfer, and all other procedures and processes.
2. Conduct training sessions and contribute training materials to the study manuals of procedures.
3. Provide or facilitate the acquisition of equipment and materials, including specifying brands, sizes, and suppliers as applicable.
4. Establish procedures for data entry and transfer of data to CoC.
5. Develop procedures for the internal as well as external quality control, and provide periodic reports on the quality control surveillance.
6. Provide long-term storage of reserve specimens or materials as directed by the Steering Committee and NIH policy for use in ancillary or future studies.

**CONFIDENTIAL**

Each director represents the laboratory or center at RISE Steering Committee meetings, on Steering Committee conference calls, and on other conference calls where the director's participation is deemed necessary.

### ***11.3 Training and Certification***

During the start-up period, clinic staff will receive central training and certification at a training workshop held by the study group. The CoC staff and selected clinical center staff with expertise in various study components will provide instruction in all aspects of the study. The purpose of the training workshop is to provide training for study staff in order to insure that the study is conducted in a standardized manner across all participating centers. The training, based on the study manual of procedures, includes review of study design, focus on eligibility criteria, subject follow-up schedule and assessments, physical, metabolic measurements, processing and shipment of specimens, use of data entry software and electronic forms, transferring data to the CoC, maintaining patient and data confidentiality, and patient treatment guidelines.

Prior to being allowed to recruit participants, each clinical center must pass certification criteria, including satisfactory participation in training as above, and supplying the CoC with an IRB approval letter and stamped informed consent forms.

Throughout the study, new staff will be trained at the appropriate clinical center and by CoC staff where appropriate. Clinic staff will re-certify annually on identified procedures. Records of certifications and training will be maintained at the clinical sites.

### ***11.4 Site Visits***

The Steering Committee will be responsible for ongoing monitoring of the performance of study components.

There are two types of site visits that can be conducted (1) scheduled monitoring and (2) as needed to address specific problems.

The RISE Study does not anticipate scheduled monitoring site visits.

If necessary, site visits will be conducted to address specific problems at a clinical center. Depending on the specific issues, site visits will be attended by the study chair or designee, the NIDDK project office, the CoC, clinical center coordinators, and others as needed. Each visit will follow a predetermined format and site visitors will complete a checklist to record findings. The site visit team will review study procedures and compare data collection records to listings from the central database. A formal site visit report will be provided to the clinical center and to the

**CONFIDENTIAL**

RISE Executive Committee to aid in correcting any issues found, and a follow-up site visit will be conducted if necessary.

## **11.5 *Study Website***

The CoC maintains the study website, which is a secure site requiring a user ID and password combination for access. The web server utilizes the Secure Socket Layer (SSL) protocol that encrypts all traffic to and from the server. Investigators, coordinators, consultants, and other study staff who would benefit from access to the information on the website are each given a unique user ID and password, which identifies the user to the web server and can be used to restrict access to particular web pages if desired.

The website contains study documents such as the protocol, manual of procedures, and forms, study calendar, directory, meeting and conference call information, links to other sites, tracking reports, minutes, and agendas.

## **11.6 *Conflict of Interest Policy***

The RISE Study investigators have adopted a conflict of interest policy similar to that used by other NIDDK collaborative groups. On an annual basis or whenever there is a significant change in status, RISE collaborators are required to disclose any financial or related interest that could present an actual conflict of interest or be perceived to present a conflict of interest. Disclosure is required to protect each individual's reputation and career from potentially embarrassing or harmful allegations of inappropriate behavior, and to protect the integrity of RISE Study research. Conflict of interest forms are kept on file at the CoC, and all conflicts are declared at each study group meeting.

The RISE Ethics Committee (NIDDK Project Scientist, NIDDK Program Official and study group member) determines (1) if the disclosed interests could directly and significantly affect the performance of study responsibilities and (2) the actions needed for management, reduction, or elimination of the conflict. In addition to complying with the RISE conflict of interest policies, collaborators must certify to the Ethics Committee that they have complied with all of their local and institutional requirements regarding conflict of interest and disclosure. This is accomplished by supplying the CoC with copies of the local IRB letter of approval and stamped informed consent form(s). Should an institution make a determination regarding an investigator's potential conflict of interest that could affect participation in RISE, the local clinic should report this to the RISE Executive Committee.

**CONFIDENTIAL**

## ***11.7 Publications and Presentations Policy***

The Publications and Presentations Subcommittee (PPS) will coordinate, monitor, review, and assume responsibility for overseeing the preparation of all study-wide communications (press releases, interviews, presentations (oral and posters), and publications) relating to the scientific aspects of the study. There will be no publication or presentation of study plans or results, including ancillary studies, which have not been reviewed and approved by a majority of the PPS, and for some types of communications, a majority of the Steering Committee.

With respect to publications and presentations from the RISE Study consortium, the goals of the PPS are to:

1. Ensure accurate, uniform, timely, and high quality reporting of RISE activities and results;
2. Preserve the scientific integrity of the study;
3. Safeguard the rights and confidentiality of participants;
4. Assure that the timing of publications and presentations serves the right of the public to know the results of the program without jeopardizing its conduct; and
5. Ensure that appropriate credit is acknowledged for people responsible for RISE and the data being reported and for the funding organizations.

Detailed policies are found in the Manual of Operations.

## ***11.8 Ancillary Studies Policy***

The Ancillary Studies Subcommittee will evaluate all proposals for studies that involve RISE participants and/or data that are not a part of the protocol. These studies may be done in all RISE participants or only on a subset of participants in RISE. Ancillary studies may make use of data and/or samples already collected from RISE participants or may involve the collection of new data and/or samples. The RISE Ancillary Studies Subcommittee must review all proposed ancillary studies and these must receive final approval by both the Steering Committee and DSMB. Major factors in consideration of ancillary studies will include:

- Clinical importance and scientific validity;
- Compatibility of goals with those of RISE; and
- Burden on study subjects and staff, including those at the CoC

**CONFIDENTIAL**

Approved ancillary studies will be reviewed by the DSMB. Detailed policies are found in the Manual of Operations. Ancillary studies will have to obtain funding from outside the study.

### **11.9 Protocol Amendments**

Adoption of protocol amendments requires two-thirds majority approval by voting members of the RISE Steering Committee and approval by the DSMB. The amended protocol will be resubmitted to the IRB, and the participant consent will be revised appropriately.

### **11.10 Repository for Storage and Distribution of RISE Data and Samples**

At the end of the study, de-identified research data and samples of blood and urine will be provided to the NIDDK Central Repositories, a research resource supported by the National Institutes of Health. The Repository collects, stores, and distributes biological samples and associated data from people with many kinds of disorders, from unaffected family members, and from other healthy people. The purpose of this collection is to make samples available for use in research for the study of obesity and diabetes and related complications after the RISE Study is completed. Sending samples to the Repository may give scientists valuable research material that can help them to develop new diagnostic tests, new treatments, and new ways to prevent or postpone the onset of obesity and/or diabetes.

As a component of the informed consent process, all participants will be asked to provide specific informed consent for release of data and samples to the NIDDK Repositories. Before the RISE Study investigators send data or samples to the Repository, each sample and data record will be given a code number and the data will be de-identified according to HIPAA requirements. Participants may choose to participate in RISE but not provide consent to have their samples and/or data transferred to the NIDDK Repository.

## **12 STUDY TIMELINE**

The study timeline allows for recruitment over the first 3 years of the study, which commences after all approvals have been obtained (DSMB, FDA, IRBs, CTAs or CRADAs), central study training has been performed and all study medications and supplies have been procured. Intervention and washout phases occur through the middle of year 5 and presentations and publications throughout the period of the study.

RISE Primary Outcome Analysis Plan – Adult Medication Study

Approved by RISE Steering Committee, Sept 2017

Approved by RISE DSMB, November 2017

Often the Disposition Index (DI) – insulin sensitivity * insulin response – is used as an overall measure of beta-cell function that appropriately accounts for the reciprocal relationship of insulin sensitivity and the beta-cell's insulin response. In these analyses, the DI assumes that the product of the two variables is constant within an individual at a given time, such that changes in insulin sensitivity would be mirrored by a proportional change in the insulin response. This implies that all points along the line represent the same level of metabolic function. In many instances this relationship has been demonstrated using insulin responses to be a rectangular hyperbola (by definition, the slope of the log-log relationship equal to -1.0); however, in others this relationship has just been assumed. The power calculations for RISE were based on the DI using data provided by several investigators that used methodologies that differed from those used in RISE.

During protocol development there was thus concern that relationships underlying this constant depend on the actual measures of peptide (insulin or C-peptide) release by the beta cell. In particular, the slope of the log-log relationship between secretion and sensitivity might not be equal to -1.0 for the C-peptide measures chosen for RISE as had been observed in prior studies based on insulin measures. Therefore, the protocols specifically state that the primary outcomes would be based on two different C-peptide responses (steady state and maximal) adjusted for insulin sensitivity defined as the glucose disposal rate divided by steady state insulin (aka M/I) during the hyperglycemic clamp. However, given the likely possibility that the relationship may not be a rectangular hyperbola, the protocol did not specify details of the approach to be used for the primary outcome analysis as a decision would be based on evaluation of the baseline data.

During analysis of the baseline data, we found that the DI (i.e. sensitivity x secretion) is sometimes paradoxically lower in pediatric participants than adult participants, despite the fact that the insulin sensitivity vs. C-peptide curves describing the relationship between these two variables appears higher in children. This contradictory finding is at least in part due to the fact that the range of values for insulin sensitivity among children is narrow compared to that of adults, i.e., children are more insulin resistant than adults. Further, the log-log slopes of insulin sensitivity vs. C-peptide responses are not equal to -1 in children or adults (or overall). Although the untransformed data show a clear inverse relationship typical of a hyperbolic curve, the slopes for each of the primary outcome measures on the log scale is approximately -0.3 (not -1.0 as may have been expected); this is a hyperbola but not a square hyperbola. Thus, the approach of performing the primary outcome analysis comparing treatment groups after washout, with a test of difference in DI at Month 15 adjusted for baseline, may not be appropriate and needed to be reassessed.

Several options were considered including a simple linear regression model (on a log scale) of C-peptide (and insulin) release as a function of insulin sensitivity, with a term for treatment group and adjusting for both variables at baseline. However, this was also deemed inappropriate because that model would estimate the difference in C-peptide (and insulin) release between groups assuming that there was no difference in insulin sensitivity between groups. Rather, we want to account for movement of both variables simultaneously without forcing a specific relationship between them. This can be accomplished by performing the primary outcome analysis using two separate models: insulin sensitivity at Month 15 vs. treatment arm (adjusted for baseline) and C-peptide (and insulin)

release at Month 15 vs. treatment arm (adjusted for baseline), where the two models are fit simultaneously using Seemingly Unrelated Regression techniques¹⁻⁵. This provides an estimate of the treatment group difference in insulin sensitivity as well as the treatment group difference in the release of the beta-cell peptides, while allowing for the correlation among the insulin sensitivity and peptide release measures. This yields an estimate of the joint covariance structure of the two models, and allows a joint statistical test of both variables using a 2-DF chi-square test of the treatment arm difference in each model. Thus, we will be able to test whether both the insulin sensitivity and C-peptide (and insulin) release variables are different across treatment groups at Month 15, adjusted for their baseline value.

This approach will provide a clear answer to the question of whether the Month 15 result differs by treatment, adjusting for baseline measures. However, given that an underlying reciprocal relationship is expected, it is possible that a significant difference could be found between groups, but that this represents a proportional shift without a specific improvement in peptide release adjusted for sensitivity. In other words, the data points could lie on a different part of a shared relationship curve such that the change represents a mutually compensated change in these terms without a separate underlying change in beta-cell function. Therefore, if the results of the two model analysis are significant, further analysis will evaluate the patterns of change in either or both variables within each group.

Below is sample Primary Outcome R code for this primary analysis.

R code and sample output for primary outcome with Seemingly Unrelated Regression model using systemfit

```
> fit12=systemfit(list(Eq1 = log_mi ~ Treatment + log_mi_base,
  Eq2 = log_cpeptide_steady ~ Treatment +
  log_cpeptide_steady_base),
  method='SUR',
  data=RISEM15)

> linearHypothesis(fit12,test = "Chisq",
  c('Eq1_TreatmentTreat2=0','Eq2_TreatmentTreat2=0'))

Hypothesis: Eq1_TreatmentTreat2 = 0      Eq2_TreatmentTreat2 = 0

Model 1: restricted model
Model 2: fit12

  Res.Df   Df   Chisq     Pr(>Chisq)
1    xxx
2  xxx-2   2   xxxx   x.xxx ← pvalue for the 2-DF joint statistical test
of both sensitivity and secretion variables of the treatment arm
difference
```

References:

1. https://en.wikipedia.org/wiki/Seemingly_unrelated_regressions

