### **3.2 Primary Outcomes**

The primary objective of the RISE Study is to evaluate the effects of randomized treatment on  $\beta$ -cell function, measured by hyperglycemic clamp techniques. Given that insulin and C-peptide are both used in quantifying  $\beta$ -cell function, each of them will be measured in certain or all tests in part to avoid the problem of collinearity when performing the statistical analyses.

Two co-primary outcomes are specified:

- $\beta$ -cell function measured as the **second phase response (steady-state of the hyperglycemic clamp)** (100-120 minutes of glucose infusion) [64]. This will be calculated as mean C-peptide at steady state, adjusted for insulin sensitivity using the hyperglycemic clamp-derived measure of insulin sensitivity (glucose disposal rate/insulin: GDR/I).
- $\beta$ -cell function measured as **AIRmax (arginine-induced acute insulin response at hyperglycemic glucose;  $\beta$ -cell secretory capacity)** [30]. This will be calculated as the incremental area under the C-peptide curve from 0-10 minutes following arginine injection at a plasma glucose  $\geq 450$  mg/dl, adjusted for insulin sensitivity measured by the hyperglycemic clamp.

Overall, for primary and secondary outcomes we will use the insulin sensitivity measured during steady state of the hyperglycemic clamp (glucose disposal rate [derived from the steady state glucose infusion rate] divided by steady state plasma insulin concentration 100-120 min) for adjustment of  $\beta$ -cell function measures [69].

The main analysis will evaluate the effect of study treatments to induce durable improvement in these primary outcome measures of  $\beta$ -cell function, by comparing each treatment against placebo following a 3-month medication washout. The study will be analyzed under the intention-to-treat principle.

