**CONFIDENTIAL**

## ***9.1 Primary Outcome and Analyses***

Two primary outcomes each measuring  $\beta$ -cell function after 3-months of washout will be assessed for this trial. In order to maintain a study-wide  $\alpha=0.05$ , a closed testing procedure will be used to assess the primary outcome [89]. The closed testing procedure is a method of hierarchical testing which tests higher-order comparisons before allowing lower-level comparisons, thus controlling the type I error and preserving power. First,  $\beta$ -cell function will be compared across the four treatment groups using an analysis of covariance model adjusted for baseline  $\beta$ -cell function. From this model, the overall test of equality across the four treatment groups will be computed. If that overall test is significant at the  $\alpha=0.05$  level, then each of the four possible sets of three interventions will be compared in four separate analysis of covariance models. The final significance testing of any set of two treatment groups is only undertaken if the p-values for each of the two 3-intervention tests which include a particular two intervention group are both  $p<0.05$ . For example, for interventions  $I_1$ ,  $I_2$ ,  $I_3$  and  $I_4$ , the first analysis of variance test  $I_{1234}$  assesses whether there are any differences among the four groups. If the overall test across the four groups is not significant, testing concludes and no treatment group is declared different from any other. Alternately, if that initial 4-group test is significant at the  $\alpha=0.05$  level, four separate analysis of covariance models with combinations  $I_{123}$ ,  $I_{124}$ ,  $I_{134}$  and  $I_{234}$  are tested. The comparison  $I_{12}$  is only tested if both  $I_{123}$  and  $I_{124}$  are significant at  $p<0.05$  and so forth. The closed testing procedure is chosen as the primary outcome analysis to maintain an overall study-wide  $\alpha=0.05$  while preserving power and allowing each set of interventions to be compared under pre-specified circumstances. The two primary outcomes will be analyzed separately with a total type I error probability of 0.05 for each, i.e. without an adjustment for two separate outcomes.

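### The SAP defines only a 2-DF test, which in a four-arm trial is one pairwise contrast, and does not say whether or how the closed procedure of protocol 9.1 carries over to the SUR model

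*SAP*

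**What the plan says.** Protocol 9.1 states that "a closed testing procedure will be used to assess the primary outcome". It starts with a single ANCOVA test of equality over four arms: "If the overall test across the four groups is not significant, testing concludes and no treatment group is declared different from any other". If that test is significant at 0.05, "each of the four possible sets of three interventions will be compared in four separate analysis of covariance models". A pair of arms is tested only when both three-arm tests containing it have p<0.05. The error level is set per outcome: "The two primary outcomes will be analyzed separately with a total type I error probability of 0.05 for each", "without an adjustment for two separate outcomes". Section 3.2 describes the main analysis as evaluating durable improvement "by comparing each treatment against placebo following a 3-month medication washout".

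The SAP for the Adult Medication Study, approved in 2017, drops the single sensitivity-adjusted measure. It fits two regressions jointly, one for log M/I and one for log C-peptide, each adjusted for its own baseline. It says this "allows a joint statistical test of both variables using a 2-DF chi-square test of the treatment arm difference in each model" and concludes that the analysis shows whether both variables differ among the treatment groups at Month 15. The sample code passes two restrictions to the test, "c('Eq1_TreatmentTreat2=0','Eq2_TreatmentTreat2=0", which is one arm's coefficient in each equation. The SAP gives no alpha and no number of comparisons, does not mention closed testing, and shows no other test.

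**The concern.** In a two-arm trial, a 2-DF joint test of two equations is the complete treatment test. In a four-arm trial it compares one arm with one other. The SAP's description of its test and the test itself therefore do not match, and nothing in the SAP corresponds to the first two levels of 9.1.

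Those two levels are what protect the 0.05. They are written in 9.1 as ANCOVAs of a single sensitivity-adjusted measure, and the SAP says a baseline-adjusted test of the disposition index may not be suitable. An analyst who wants to keep the closed procedure must therefore choose the higher-level tests: joint SUR tests, the ANCOVAs of 9.1, or none. The same data could then let an arm be declared better than placebo under one choice and leave it untestable under another. That choice should not be open once results by arm are known.

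**Working it through.** **Inputs.** Four arms of about equal size, with 56 per arm at the end of washout (protocol 3.7 and 9.3). Three comparisons with placebo (3.2). Alpha 0.05 per outcome (9.1). Two equations per outcome (SAP). All error rates below are under the global null.

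**1. The protocol's own figure.** Simulating the four-arm, three-arm and pair steps of 9.1 with one variable per arm (1,000,000 replicates) gives 5.0% rejection at the four-arm test, 4.9% for any pair declared different, and 3.3% for any placebo comparison. The stated 0.05 reproduces. For the three placebo comparisons the steps form a complete closure: two placebo nulls together are a three-arm null, and all three together are the four-arm null.

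**2. Degrees of freedom under SUR.** DF = (arms compared − 1) × equations.
- Four arms: 3 × 2 = 6
- Three arms: 2 × 2 = 4
- Two arms: 1 × 2 = 2

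The SAP's test is the last of these only.

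**3. Error if three 2-DF placebo tests are run with no prior step.** The critical value is c = −2 ln 0.05 = 5.991. The Wald statistic is unchanged by linear transformation of the two variables, so in large samples the correlation between equations drops out. Let r be the length of the standardised placebo estimate. Given r, each active arm escapes rejection with probability F(2c; 2, r²), the non-central chi-square distribution function with 2 DF and non-centrality r². The arms are independent given r, so

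FWER = 1 − ∫₀^∞ r·exp(−r²/2)·[F(2c; 2, r²)]³ dr = 0.1271.

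Checks:
- Large-sample simulation gives 12.7%.
- Ignoring the shared control gives 1 − 0.95³ = 14.3%, which is an upper check.
- The same calculation with 1-DF tests gives 12.5%, so the inflation comes from omitting the higher-level tests and not from using SUR.
- A finite-sample SUR simulation (56 per arm, 4,000 replicates) gives 14.0%, Monte Carlo SE 0.5. It assumed a residual correlation of −0.3 between equations, which the documents do not give, and the baseline correlation of 0.57 from 9.3. A single 2-DF test rejected 5.55% of the time in that run, so part of the excess over 12.7% may be small-sample liberality of the Wald test.

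**4. Error if 9.1 is carried over with 6-, 4- and 2-DF tests.** Large-sample simulation (1,000,000 replicates):

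| Event | Rate |
|---|---|
| Four-arm 6-DF test rejects | 5.0% |
| Any pair declared different | 4.5% |
| Any placebo comparison declared different | 3.0% |

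In the finite-sample run the 6-DF test rejected 5.4% of the time, and a false placebo comparison occurred in 3.0%.

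**The case against.** The strongest reply is that the SAP changes the outcome model and nothing else. Its stated reason is the log-log slope of about −0.3 between sensitivity and C-peptide, which has no bearing on multiplicity. No sentence in it withdraws 9.1. The code is labelled as a sample and shows only the steady-state C-peptide outcome; if omission from the sample meant repeal, the AIRmax co-primary would be gone too, and the SAP plainly keeps both. A single-arm 2-DF call is also what the pair step of 9.1 would look like under SUR. On this reading the protocol supplies the decision rule, the SAP supplies the model, and error stays at 5%.

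Most of this stands. A reader might infer that the closed procedure has been abolished and that the trial's error is about 13%. The documents do not support that: the SAP is silent, and it sets no alpha at which unrestricted tests would be run. A reader might also want to combine the error over both co-primary outcomes. That would charge the SAP with inflation the protocol accepts openly, since 9.1 makes no adjustment across outcomes.

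Two things do not stand. The 2-DF statement is in the SAP's prose as well as its code, and the prose presents it as a test among the treatment groups, which it cannot be with four arms. And 9.1 cannot be applied to the new model without further decisions, because its four-arm and three-arm tests are defined only for the ANCOVA.

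**Conclusion.** The SAP does not say whether or how the closed procedure of 9.1 applies to the SUR tests, and it describes a pairwise test as if it covered all the groups. The consequence is conditional. If the SAP's test is run as written for each active arm against placebo at 0.05, the family-wise error is about 12.7% per outcome (14.0% in the finite-sample simulation) against a stated 5%. If 9.1 carries over with joint tests of the right size, the four-arm test holds 5.0% and a false placebo comparison occurs in about 3%.

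These figures assume equal arms and the global null. The 12.7% is a large-sample value that does not depend on the correlation between equations; the 14.0% rests on the assumed −0.3. The 5% protection under 9.1 applies to the placebo comparisons. Across all six pairs, 9.1 has no step for two disjoint pairs, and the error can reach 9.8% when the arms split two and two. That is a property of 9.1 itself and does not affect the comparisons with placebo.

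**What to change.** State in the SAP, before Month 15 results are compared by arm, that SUR replaces ANCOVA inside the closed procedure of 9.1, separately for each co-primary outcome at 0.05:

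1. Four arms: test all three arm coefficients in both equations jointly (6 DF).
2. If p<0.05, fit SUR to each three-arm set and test its two arm coefficients in both equations (4 DF).
3. Test a pair (2 DF) only if the four-arm test and both three-arm tests containing that pair have p<0.05.

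Reword the sentence that presents the 2-DF test as covering all treatment groups. Replace the sample code with calls for all three levels, with placebo as the reference level. Say whether the robust covariance that 9.1 requires for each ANCOVA also applies to the SUR tests; the SAP does not mention it and the sample code does not request it.

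The cost is a few lines of text and code, with no new data. The downside is that fewer pairwise results will be declared significant than if pairs were tested directly.
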